10. Tumor imaging is required at baseline and then every 8 weeks (+/- 7 days) during study treatment. Unless there is a dose delay, imaging should be done within 7 days prior to odd cycles. If a patient completes 24 cycles without progression repeat imaging will be done every 3 months (+/- 7 days) from last receipt of study therapy as per section 7.7. Tumor imaging should be at minimum with a CT neck with IV contrast, CT chest with IV contrast, and CT abdomen/pelvis with IV contrast. If MRI is determined to be a better modality to follow the patients malignancy an MRI can be used. If a patient has an allergy to CT contrast dye that precludes usage than MRI can be used for disease in the head and neck and CT non-contrast can be used for the chest, abdomen and pelvis if the investigator has determined that tumor measurements can be made without the usage of CT IV contrast.

A See section 7.4 for details of treatment with Relatlimab plus Nivolumab

B For patients with progressive disease who don't qualify for a second treatment on study per section 7.6, or who are withdrawn from the study for any reason including toxicity, safety follow up will occur for patients that discontinue trial treatment for any reason 30 days (+/- 7 days) after the last dosage of study drug combination

C For patients with progressive disease who don't qualify for a second treatment on study per section 7.6, or who are withdrawn from the study for any reason including toxicity, survival follow up will occur starting 3 months after the last dosage of study drug. A call will be placed to the patient for survival status and if alive whether subsequent anti-neoplastic therapy was received. Patient will receive calls every 3 months for the first year and then every 6 months for the second year, then yearly thereafter.

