- Patient will not need to undergo repeat testing for HIV and Hepatitis B and C
- Patients will undergo serum collection for correlative studies before initiation of second treatment.

7.7 FOLLOW UP SCHEDULE FOR PATIENTS THAT COMPLETE 24 CYCLES OF THERAPY WITHOUT PROGRESSION OF DISEASE

If a patient completes all 24 cycles of therapy without progression the patient will be seen as per safety follow up visit at 30 days (+/- 7 days) and then every 3 months (+/- 7 days) from the last receipt of study therapy. Patient will undergo repeat imaging every 3 months and may be eligible for retreatment as per section 7.4 if the patient progresses.

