 - Grade 4 drug-related endocrinopathy adverse events, such as, hyper- or hypothyroidism, or glucose intolerance, which resolve or are adequately controlled with physiologic hormone replacement (corticosteroids, thyroid hormones) or glucose-controlling agents, respectively, may not require discontinuation after discussion with and approval from the Sponsor.
4. Any event that leads to delay in dosing lasting > 6 weeks from the previous dose requires discontinuation, with the following exceptions:
 - Dosing delays to allow for prolonged steroid tapers to manage drug-related adverse events are allowed. A drug related adverse event where steroids are not indicated but the management of the adverse event causes a dose delay lasting > 6 weeks may be allowed if approved by the Sponsor.
 - Dosing delays lasting > 6 weeks from the previous dose that occur for non-drug-related reasons may be allowed if approved by the Sponsor.
5. Any adverse event, laboratory abnormality, or intercurrent illness which, in the judgment of the Investigator, presents a substantial clinical risk to the participant with continued study drug combination dosing.
6. Prior to re-initiating treatment in a participant with a dosing delay lasting > 6 weeks, the sponsor must be consulted. Tumor assessments should continue as per protocol even if dosing is delayed. Periodic study

visits to assess safety and laboratory studies should also continue if clinically indicated during such dosing delays.

7. Subjects who meet criteria for permanent discontinuation should receive no further study therapy. The following exceptions apply:

- If the toxicity resolves to < Grade 1 or baseline > 6 weeks after last dose, but the subject does not otherwise meet the criteria for permanent discontinuation and the Investigator believes that the subject is deriving clinical benefit, then the subject may be eligible to resume the study drug(s) following the approval of the sponsor.
- Subjects with a grade 4 drug-related amylase and/or lipase increase that is not associated with symptoms or clinical manifestations of pancreatitis can be restarted on therapy once the levels have recovered to grade 3 or less, and after consultation with the sponsor.
- Subjects with baseline Grade 1 AST, ALT, or total bilirubin who require dose delays for reasons other than a drug-related hepatic event may resume treatment in the presence of Grade 2 AST, ALT, or total bilirubin.

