Estimate the disease control rate (DCR), progression-free survival (PFS), overall survival (OS) and safety of treatment determined by gene expression of LAG3 and CTLA4 per OmniSeq Immune Report card for R/M HNSCC patients who have progressed on prior immunotherapy. The analysis of DCR is similar to that of objective response. PFS and OS will be analyzed by means of proportional hazards (Cox) regression models including treatment and OmniSeq response score as covariates. Safety, represented by serious adverse events at least possibly related to treatment, will be analyzed in a similar fashion to the primary endpoint, where each participant will be scored as experiencing or not experiencing at least one such events. All point estimates will be accompanied by 95% credible or confidence intervals. Adverse events will also be tabulated by type, grade and relatedness to treatment.

15.2.3 SECONDARY OBJECTIVE 2

Estimate the probability of objective response, DCR, PFS, OS and safety of treatment that is randomly assigned instead of determined by gene expression. This will be compared in an exploratory fashion to the objective response of those patients with treatment determined by gene expression. The probability of objective response and DCR will be estimated by logistic regression with treatment, OmniSeq response score and treatment assignment modality (randomized versus OmniSeq) as covariates. PFS and OS will be estimated by proportional hazards (Cox) models. All estimates of odds and hazard ratios will have 95% confidence intervals.

15.2.4 SECONDARY OBJECTIVE 3

Estimate the probability of objective response, DC, PFS, OS and safety of treatment determined by gene expression of LAG3 and CTLA4 per OmniSeq Immune Report card for R/M HNSCC patients who have progressed on trial treatment and undergo a second biopsy and second treatment determined by a second gene expression analysis of LAG3 and CTLA4. The analysis is similar to those in the above aims. It is possible the numbers of participants in this category will not support these analyses, in which case descriptive statistics will be presented.

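### Progression after an early permanent stop without progression, including for toxicity, is not scheduled to be collected, and no PFS definition or censoring rule says how these patients are counted

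*Combined protocol and SAP*

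**What the plan says.** Both treatment calendars tie imaging to being on therapy: "Tumor imaging is required at baseline and then every 8 weeks (+/- 7 days) during study treatment" (section 7.2, footnote 10; section 7.3, footnote 8). Two situations off active dosing are also covered:

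- When a dose is held, section 12.3 says "Tumor assessments should continue as per protocol even if dosing is delayed".
- After the full course, the same calendar footnotes say "If a patient completes 24 cycles without progression repeat imaging will be done every 3 months". Section 7.7 repeats this for the same group: "If a patient completes all 24 cycles of therapy without progression the patient will be seen as per safety follow up visit", and "Patient will undergo repeat imaging every 3 months".

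Everyone else who leaves treatment gets a safety visit at 30 days and then telephone follow-up. Footnote C covers patients with progression who do not qualify for a second treatment, and those "withdrawn from the study for any reason including toxicity, survival follow up will occur starting 3 months after the last dosage of study drug". The content of the contact is given as: "A call will be placed to the patient for survival status and if alive whether subsequent anti-neoplastic therapy was received". Calls are every 3 months in the first year, every 6 months in the second, then yearly.

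On the analysis side, section 15.2.2 states: "PFS and OS will be analyzed by means of proportional hazards (Cox) regression models", with treatment and OmniSeq response score as covariates. The plan contains no definition of PFS and no censoring rule.

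**The concern.** A patient who stops for toxicity while progression-free leaves the imaging schedule and enters a follow-up that does not ask about progression. The progression date, which PFS needs, then has no planned source. The reason for the loss is treatment-related, so it cannot be assumed to be ignorable. If toxicity stops are more common with one regimen, the loss also falls unevenly on the treatment term in the Cox model. With no PFS rule in the SAP, the handling of these patients would be chosen at analysis, possibly with the data in view.

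**Working it through.** **1. Which patients have a planned route to a dated progression**

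| Patient's situation | Imaging planned? | Source |
|---|---|---|
| On study treatment | Every 8 weeks | 7.2 fn 10, 7.3 fn 8 |
| Dosing delayed | Continues | 12.3 |
| Completed 24 cycles, no progression | Every 3 months | 7.2, 7.3, 7.7 |
| Stopped permanently before 24 cycles, no progression | None stated | footnotes B and C give a 30-day safety visit, then calls |

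The call in footnote C has two items: survival, and whether new therapy was received. It does not list progression, and it does not list the date of new therapy.

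**2. What the analysis could do with the fourth group**

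The SAP does not say, so there are two natural outcomes.

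- Censor at the last scan. This is unbiased only if the later progression risk of those who stopped matches that of those who continued.
- Count the death reported at a later call. The event is then dated after the true progression, so PFS is too long.

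**3. How many patients**

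The documents give no PFS event count or dropout rate, so there is no stated figure to reproduce.

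- Table 9 (15.3.2) pauses at 7 or more of 30, so 6 of 30 = 20% may stop for adverse events without a pause. 0.20 × 40 = 8. That is a ceiling at this rate, reached only if nobody who stops has already progressed.
- Section 2.4.6 cites discontinuation rates with ipilimumab plus nivolumab of 22% (renal) and 36.4% (melanoma). Applied to all 40 these give 8.8 and 14.6, but only part of the trial receives ipilimumab.
- With 20 ipilimumab patients: 20 × 0.22 = 4.4 and 20 × 0.364 = 7.3. Using Table 7 at 15.2 (4 assigned to ipilimumab plus half of 11 randomized, of 16): 9.5/16 = 59%, or 23.75 of 40, giving 5.2 and 8.6. No overall discontinuation rate for relatlimab plus nivolumab is given.

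**4. Illustration of the effect on median PFS**

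Every input here is an assumption:

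- Exponential PFS with median *m* of 2.5 or 4.0 months, hazard ln 2 / *m*.
- 10%, 20% or 36% of patients at risk of a toxicity stop, at a time uniform on 0.5 to 4 months. The stop occurs only if it precedes progression.
- Progression hazard after the stop multiplied by *r* = 0.5, 1 or 1.5.
- Death a mean of 5 months after progression.
- 200,000 simulated patients per setting, so the differences show bias and not sampling error. The 8-week scan grid is ignored.

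| *m* | At risk | *r* | Stopped before progression, of 40 | True median | Censored at stop | Later death as event |
|---|---|---|---|---|---|---|
| 2.5 | 10% | 0.5 | 2.2 | 2.53 | 2.50 (−0.03) | 2.57 (+0.04) |
| 4.0 | 20% | 0.5 | 5.5 | 4.21 | 4.00 (−0.21) | 4.46 (+0.25) |
| 4.0 | 20% | 1.5 | 5.5 | 3.85 | 4.00 (+0.15) | 4.34 (+0.49) |
| 4.0 | 36% | 0.5 | 9.9 | 4.41 | 3.99 (−0.42) | 5.01 (+0.60) |
| 4.0 | 36% | 1 | 9.9 | 3.98 | 3.99 (+0.01) | 4.81 (+0.83) |
| 4.0 | 36% | 1.5 | 9.9 | 3.75 | 4.01 (+0.26) | 4.69 (+0.94) |

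Over all settings, 2.2 to 9.9 of 40 stop before progression. Censoring at the stop shifts the median by about −0.4 to +0.3 months, and by essentially nothing when *r* = 1. Counting the later death overstates it by about 0.04 to 0.9 months. The 36% rows apply the highest cited rate to the whole trial and are extremes.

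**The case against.** **Other marks and terms in the plan.** Medical history is marked at survival follow-up in both calendars, so progression might be picked up there; it would be too strong to say it can never be dated. But footnote C defines that contact as a call with two items. As extracted, the 7.3 calendar shows an imaging mark under the safety visit. This looks like a column shift, since neither the imaging nor the thyroid row has a mark under later cycles, where the footnotes require both. If real, it is one scan in one regimen. Footnote C speaks of withdrawal from the study, whereas section 6.7 separately lists reasons for stopping treatment. Yet footnote B in 7.2 runs the two together, and no other pathway is given for an early stop without progression.

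**Censoring.** A reader might infer that PFS is censored at the last on-treatment scan. The SAP does not say so; a death found by telephone could equally be used as the event. Nor do the documents show that toxicity stops are related to later progression. This part of the objection stands: what is established is a missing rule and missing data, not a particular bias.

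**Primary endpoint.** A reader might also infer that responses first seen just before a stop are lost. Section 13.2 allows a confirming scan from 4 weeks if clinically indicated, and section 13.3 runs best response to progression, not to end of treatment. There is no next scheduled scan for such a patient, so confirmation is ambiguous, but a loss is not established.

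**Size.** Taking 10% to 36% of all 40, or 4 to 14 patients, as having no dated progression would be too high. The upper rates come from other tumours and apply only to ipilimumab plus nivolumab, section 2.4.7 claims better tolerability for the schedule it describes, and not every stop precedes progression.

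**Conclusion.** The gap holds for PFS. For patients who stop permanently and early without progression, the plan schedules neither imaging nor a question about progression, and it does not say how PFS treats them. Roughly 2 to 10 of 40 patients could be affected under the assumptions shown, with about 8 as the ceiling at the 20% rate that Table 9 tolerates at 30 patients. The direction of any bias is unknown if they are censored and upward if a later death is used. The treatment term in the Cox model could be distorted if stop rates differ by regimen; the documents give no overall rate for relatlimab plus nivolumab, so this cannot be sized.

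The consequence is limited. PFS is secondary and is estimated, not tested. The documents do not support reading this as an established loss of responders in the primary endpoint. It is worth correcting because the correction is cheap.

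**What to change.** - **Footnote C, sections 7.2 and 7.3:** at the existing calls, record the date and basis of any progression and the date of any new anticancer therapy. For patients who stopped without progression, obtain routine-care scan reports until progression, death or new therapy.
- **Section 15.2.2:** define PFS (start, events, how the progression date is set) and state the primary censoring rule for patients who stop early without progression. Add a sensitivity analysis that counts the start of new anticancer therapy as an event.
- **Section 13.2:** state how a response first seen shortly before a permanent stop is classified when no confirming scan follows.

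Cost: extra questions on calls already planned, collection of outside reports, a few sentences in the SAP and one more analysis. No scans are added. The downside is that routine-care scans are less regular than protocol scans, so progression dates from that source should be flagged in the data.

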7.3 STUDY CALENDAR FOR PATIENTS TREATED WITH NIVOLUMAB AND IPILIMUMAB (CYCLE=28 DAYS)

Assessments	Cycle 1		Cycle 2		Cycle 3		Cycle 4		Cycle 5		Day 1 All subsequent cycles (± 3d)	Safety F/U ^B	Survival F/U ^C
	D1	D14 (±3d)	D1 (±3d)	D14 (±3d)	D1 (±3d)	D14 (±3d)	D1 (±3d)	D14 (±3d)	D1 (±3d)	D14 (±3d)			
Administer Nivolumab ^A	X	X	X	X	X	X	X	X	X	X	X		
Administer Ipilimumab ^A	X			X			X			X			
Medical History	X		X		X		X		X		X	X	X
Medication History	X		X		X		X		X		X	X	
Physical examination	X	X	X	X	X	X	X	X	X	X	X	X	
Vital Signs and Weight ¹	X	X	X	X	X	X	X	X	X	X	X	X	
ECOG PS	X	X	X	X	X	X	X	X	X	X	X	X	
Review adverse events	X	X	X	X	X	X	X	X	X	X	X	X	
Pregnancy Test ²													
CBC w/ differential ³ ₄	X	X	X	X	X	X	X	X	X	X	X	X	
Comprehensive Metabolic Panel ⁴	X	X	X	X	X	X	X	X	X	X	X	X	
TSH, FT4, T3 ⁵	X						X ⁵					X ⁵	
Tumor Tissue ⁶													
Biomarker Studies/ Microbiome ⁷	X				X								
Tumor Imaging ⁸					X							X ⁸	

1. Vital signs to include temperature, pulse, respiratory rate, blood pressure. Height will be recorded at screening visit only.
2. For women of reproductive potential, a urine pregnancy test will be performed within 1 day prior to first dosage of study drugs. If a urine pregnancy result can't be confirmed as negative, then a serum pregnancy test will be required. Pregnancy testing may be repeated if pregnancy is suspected.
3. CBC to include white blood cells, hgb/hct, platelets and differential.
4. CBC and CMP will be done at scheduled visits every 2 weeks for the first 5 cycles and then prior each cycle of study drug therapy. These labs can be obtained up to 72 hours prior to study therapy. Chemistry tests to include sodium, Potassium, Chloride, CO2, Glucose, BUN, Creatinine, Calcium, total Protein, Albumin, AST, ALT, Alkaline Phosphatase, Total Bilirubin, Magnesium, and Phosphorus
5. Thyroid function tests (TSH, Free T4, Total T3) will be done prior to every 3rd cycle or more frequently at the discretion of the treating physician
6. If a patient undergoes a second biopsy on trial for potential retreatment a new biopsy (core or surgical/incisional/excisional) will need to be obtained. See section 7.6
7. Blood will be drawn for correlative studies. Instructions on tubes needed for biomarkers study blood draws are in section 14.0. They will be drawn prior to first dosage of study drug combination C1D1, and C3D1 prior to infusion, and at next study visit after progression is confirmed. Microbiome studies as per section 14.0 will also be obtained at these same timepoints.
8. Tumor imaging is required at baseline and then every 8 weeks (+/- 7 days) during study treatment. Unless there is a dose delay, imaging should be done within 7 days prior to odd cycles. If a patient completes 24 cycles without progression repeat imaging will be done every 3 months (+/- 7 days) from last receipt of study therapy as per section 7.7. Tumor imaging should be at minimum with a CT neck with IV contrast, CT chest with IV contrast, and CT abdomen/pelvis with IV contrast. If MRI is determined to be a better modality to follow the patients malignancy an MRI can be used. If a patient has an allergy to CT contrast dye that precludes usage than MRI can be used for disease in the head and neck and CT non-contrast can be used for the chest, abdomen and pelvis if the investigator has determined that tumor measurements can be made without the usage of CT IV contrast.

A See section 7.5 for details of treatment with Ipilimumab plus Nivolumab

B For patients with progressive disease who don't qualify for a second treatment on study per section 7.6 or who are withdrawn from the study for any reason including toxicity a safety follow up will occur 30 days (+/- 7 days) after the last dosage of study drug combination

C For patients with progressive disease who don't qualify for a second treatment on study per section 7.6, or who are withdrawn from the study for any reason including toxicity, survival follow up will occur starting 3 months after the last dosage of study drug. A call will be placed to the patient for survival status and if alive whether subsequent anti-neoplastic therapy was received. Patient will receive calls every 3 months for the first year and then every 6 months for the second year, then yearly thereafter.

7.4 TREATMENT WITH RELATLIMAB PLUS NIVOLUMAB

Nivolumab will be dosed 480mg IV q 28 days and Relatlimab 160mg IV q 28 days, as per section 8.0. Therapy will be given every 28 days (+/- 3 days) and one cycle is defined as 28 days. During treatment the patient will be seen at least every 2 weeks by the treating physician in addition to the day of the cycle during the first 2 cycles than at least monthly on the day of the cycle, starting after the 3rd cycle. Patients will be treated with up to 24 cycles or until progression or discontinuation of study therapy for adverse events or any other reason, whichever occurs first. Repeat imaging will be done prior to (within 7 days) every 3rd cycle of therapy. If a patient completes 24 cycles without progression repeat imaging will be done every 3 months (+/- 7 days) from last receipt of study therapy as per section 7.7. Anytime during the course of treatment or after completion of 24 cycles if the patient is found to have progression the patient may be eligible for a second biopsy and second treatment if they meet eligibility criteria as detailed in section 7.6.

7.5 TREATMENT WITH IPILIMUMAB PLUS NIVOLUMAB

A cycle of therapy will be defined as 28 days of treatment. Nivolumab will be dosed at 3mg/kg IV q 14 days (+/- 3 days) and Ipilimumab 1mg/kg IV q 42 days (+/- 3 days). Patients will receive four doses of Ipilimumab and the last dosage of Nivolumab 3mg/kg IV q 14 days will be given at the time of the 4th dose of Ipilimumab (C5D14), followed 2 weeks later by Nivolumab 480 mg IV q 28 days which will be C6D1. Nivolumab 480mg IV q 28 days (+/- 3 days) will be given for the remainder 19 cycles for total of 24 cycles. The patient will be seen every 2 weeks during the first 6 cycles and then every 4 weeks after the 6th cycle is received. There is a +/- 3 day window for each dosage of Nivolumab and Ipilimumab. Patients will be treated with up to 24 cycles or until progression or discontinuation of study therapy for adverse events or any other reason, whichever occurs first. Repeat imaging will be done prior to (within 7 days) every 3rd cycle of therapy. If a patient completes 24 cycles without progression repeat imaging will be done every 3 months as per section 7.7. Anytime during the course of treatment or after completion of 24 cycles if the patient is found to have progression the patient may be eligible for a second biopsy and second treatment if they meet eligibility criteria as detailed in section 7.6.

7.6 CRITERIA FOR A SECOND BIOPSY AND SECOND TREATMENT ON TRIAL

If a patient progresses anytime during the course of treatment or after completion of 24 cycles they may be potentially eligible for a second biopsy and second treatment based on gene expression of LAG3 and CTLA4 per OmniSeq Immune Report Card on trial if the following criteria are met:

1. Has not been treated for recurrence/disease progression with other anti-cancer treatment.
2. Still meets all inclusion/exclusion criteria with the exception of exclusion criteria #2.

If patient meets the above criteria they can undergo a repeat biopsy and analysis by OmniSeq immune report card for immune gene expression. If a patient progresses during study therapy and has received Ipilimumab and Nivolumab initially (either via selection based on gene expression or randomization) then expression of LAG3 must be greater (criteria as per treatment assignment rule) than CTLA4 for a patient to stay on trial and receive Relatlimab and Nivolumab. If a patient has received Relatlimab and Nivolumab initially (either via selection based on gene expression or randomization) then gene expression of CTLA4 must be greater than LAG3 (criteria as per treatment assignment rule) for a patient to stay on trial and receive Ipilimumab and Nivolumab. If a patient undergoes a second biopsy and he/she does not meet the minimum required difference in relative rank score between CTLA4 and LAG3 as per the treatment assignment rule, than the patient will be taken off of study (will not be randomized to treatment). If a patient completes all 24 cycles of therapy without progression but then recurs within 3 months discontinuation of therapy than the ability to receive retreatment is the same (as described above) as for patients that progressed on study therapy. If the patient progresses after 3 months after completion of all 24 cycles than retreatment can be with the same combination received prior of that gene expression marker is highest on repeat biopsy. Patients that meet criteria for retreatment can be treated for up to 24 additional cycles with this second treatment with dosing and schedule the same as per section 7.2 and 7.3 above.

These patients will undergo trial screening procedures as per Section 7.1, with the following exceptions:

- Patients will not have to sign another informed consent document.

- Tumor imaging will need to be repeated if last imaging was greater than 28 days ago
- Patient will not need to undergo repeat testing for HIV and Hepatitis B and C
- Patients will undergo serum collection for correlative studies before initiation of second treatment.

7.7 FOLLOW UP SCHEDULE FOR PATIENTS THAT COMPLETE 24 CYCLES OF THERAPY WITHOUT PROGRESSION OF DISEASE

If a patient completes all 24 cycles of therapy without progression the patient will be seen as per safety follow up visit at 30 days (+/- 7 days) and then every 3 months (+/- 7 days) from the last receipt of study therapy. Patient will undergo repeat imaging every 3 months and may be eligible for retreatment as per section 7.4 if the patient progresses.

